3.0 Objectives

- Describe the study's purpose, specific aims, or objectives.
- State the hypotheses to be tested.
- Indicate the relevance to Veterans and the VA

The primary hypothesis is that anxiety outcomes, as measured by the GAD-7, and quality of life, measured by the SF-12 will be superior at 4-, 8-, and 12-month follow up for patients who are assigned to receive bCBT vs. EUC.

Primary Aim: To determine whether anxiety symptoms (GAD-7) and quality of life (SF-12) differ as a function of the intervention (bCBT for anxiety vs. EUC) at 4-, 8-, and 12-month follow-ups.

Secondary Aims: (Prediction of bCBT response and VVC-H use (bCBT group only)): A) To identify factors associated with bCBT response, namely whether bCBT is effective for specific anxiety disorders (e.g. generalized anxiety, panic, social phobia) and whether number of sessions received, and treatment engagement are critical to outcomes. B) To identify Veteran demographic and clinical factors associated with VVC-H use.

Exploratory Aims: A mixed-methods formative evaluation, informed by RE-AIM QuEST, will collect data related to Reach (#of Veterans receiving bCBT and VVC-H), Effectiveness (bCBT and VVC-H impact), Adoption (# of providers using bCBT and VVC-H), and Implementation (provider bCBT program fidelity and VVC-H potential). Data will be collected from qualitative interviews with Veterans and providers and integrated with quantitative data from provider surveys and chart reviews of bCBT and VVC-H use. With the ORD supplement to the main project, [name] will leverage the diverse Veteran populations included in the multisite

parent study (Houston, San Antonio, and New Orleans VA MCs) to understand barriers to treatment and research access for African American and Hispanic Veterans.

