5.6 Data Analysis

- Provide sample size determination and analysis (include anticipated rate of screen failures, study discontinuations, lost to follow-up etc.).
- Describe how, where and by whom the data will be analyzed.

Primary aim: Anxiety and Quality of Life differ as a function of bCBT for anxiety vs. EUC:

All analyses will be done on an intention-to-treat basis, and participants will be analyzed in the group to which they were randomized. We will first determine whether participants randomized

to the two study arms differed on baseline characteristics, age, race, gender, medical or mental health comorbidities, and anxiety. Chi-square tests will be used for categorical variables and t-test for continuous and ordinal variables.

We will examine the normality of the distributions of both primary outcomes and will consider transformations such as the log or the inverse. Because we are using an unequal randomization (see sample size section), it is especially important to test the assumption about the homogeneity of the variance of the residuals across the levels of the independent variables³⁷. For analyses of our primary outcomes, we will test the homogeneity assumption before testing for differences between the bCBT and EUC groups. If the assumption of equal variances is violated, we will use statistical tests such as the approximate t-test, which uses individual sample variances instead of the pooled variance. In addition, we will obtain Satterthwaite's approximation of the degrees of freedom. For the regression models, we will test whether the residual variances are equal and, if necessary, we will fit unequal variance models to obtain better estimates of the standard errors of the difference between groups. We will calculate the absolute differences in outcome measures between baseline and 12-month follow-up and the effect sizes of the bCBT group compared with EUC. We will also examine effect sizes for the bCBT group baseline vs. post-treatment and 8-month follow-up.

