Analyses will use data from the mixed-method formative evaluation described above. Qualitative pre-implementation data will be analyzed using rapid qualitative analysis, a systematic and rigorous process, to provide data in real-time to tailor the intervention, and identify contextual barriers prior to rollout^{38,39,40}. Implementation and post-implementation interviews with providers and Veterans will be analyzed using directed content analysis⁴¹ consisting of deductive (a priori) codes from the RE-AIM QuEST framework. Inductive (a posteriori) codes that emerge from providers' and Veterans' experiences with the intervention and VVC-H delivery will also be identified. We will utilize Atlas.ti software to facilitate analysis and management of qualitative data. Quantitative data will be collected and analyzed as descriptive data.

Sample Size and Power Calculations

Primary Aim: To determine whether anxiety symptoms (GAD-7) and quality of life (SF-12) differ as a function of the intervention (bCBT for anxiety vs. EUC) at 4-, 8-, and 12-month follow-ups. A three-step sample-size calculation indicates that 225 anxiety patients will need to be randomized to draw conclusions regarding the primary hypothesis that bCBT will be superior to EUC at 4-, 8, and 12-month assessments.

Step 1: Power to detect GAD-7 differences. A sample size of 138 anxiety patients is needed to detect an effect size = 0.38 for the differences between bCBT and EUC GAD-7 outcomes using a two-sided t-test with 80% power at the .05 significance level, adjusted for repeated measures³⁷. The formula for the sample size, adjusting for repeated measures, is

$$N = \frac{2 * (Z_{(1-\alpha/2)} + Z_{(1-\beta)})^2 [1 + (T - 1) \rho]}{d^2 T}, \text{ where } N \text{ is the sample size per group, } Z_{(1-\alpha/2)} \text{ and}$$

$Z_{(1-\beta)}$ are the $(1-\alpha/2)$ and $(1-\beta)$ percentiles of the normal distribution, T is the number of follow-up measures, ρ is the correlation coefficient of the repeated measurements, and d is the effect size⁴². Solving this with $T = \text{three follow-up measurements after baseline}$, $d = 0.38$, and $\rho = .7$ yields a sample size per group of 69, and total sample $N^t = 138$.

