Quality of Life Outcomes. Our prior study of patients with anxiety or depression¹⁰ resulted in mean, standard deviations, and effect size of 7, 11, and 0.3 respectively for the SF12V mental component score (MCS). SAS[®] proc power indicated that a two-sided t-test with 80% power at the .05 significance level requires a sample of 40 patients per group (80 total). Because the sample required for the anxiety measure (GAD-7; $n=138$) is greater than that needed for the

quality-of-life measure (SF12V; n=80), adjusting for repeated measures, unequal sample, and clustering on provider is presented below for the anxiety measure.

Step 2: Unequal Randomization. To increase power for the project's secondary and implementation outcomes and to reduce unnecessary recruitment, unequal allocation will be used where approximately 60% of Veterans will be randomized to bCBT. As noted by Dumville et al.³⁷, an unequal number of participants per group is an under-used technique that offers advantages for randomized trials, most notably, reduction in unnecessary recruitment. Revised total sample size $N' = N(1+k)^2/4k$, where $N=138$ and $k=1.5$, which gives revised total sample $N'=145$. The individual sample size in each of the two groups are $N'/(1+k)$ and $kN'/(1+k)$; giving $n=58$ in the EUC group and $n=87$ in the bCBT group.

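### Step 1 gives power for the GAD-7 difference averaged over months 4, 8 and 12, but the plan states the powered hypothesis by visit and names no test of that average

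*Protocol*

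**What the plan says.** **Hypothesis.** Protocol 3.0 (Objectives) states that GAD-7 and SF-12 outcomes "will be superior at 4-, 8-, and 12-month follow up for patients who are assigned to receive bCBT vs. EUC". Protocol 5.6 (Sample Size and Power Calculations, Primary Aim) ties the sample size to the same statement: 225 patients are needed "to draw conclusions regarding the primary hypothesis that bCBT will be superior to EUC at 4-, 8, and 12-month assessments".

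**Sizing.** Step 1 sets the standardised GAD-7 difference between arms at 0.38 and describes the calculation as made "using a two-sided t-test with 80% power at the .05 significance level, adjusted for repeated measures". In its formula "T is the number of follow-up measures", set to three, and the correlation of repeated measurements is .7. The result is 69 per group, 138 in total. Steps 2 and 3 turn this into 145 bCBT and 80 EUC through 1.5:1 allocation, a 1.25 inflation for provider clustering in the bCBT arm, and 25% attrition at one year.

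**Analysis.** Protocol 5.6 (Primary aim) and the SAP use the same text. One element is a 12-month quantity: "We will calculate the absolute differences in outcome measures between baseline and 12-month follow-up", with between-arm effect sizes. The other is a mixed model over baseline and the three follow-ups, which fits a line for each participant and puts most weight on the time-by-treatment interaction. A t-test appears in connection with unequal variances, but it is not tied to any visit or summary.

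**The concern.** A power statement is useful only if it refers to the test that will decide the trial. Here the quantity that is sized, the hypothesis that is stated and the term that is tested appear to be three different things. A test at one visit does not get the variance reduction that comes from averaging three visits, so the Step 1 figure overstates its power when the same inputs are used. The plan also does not say whether superiority is to be shown on average, at one named visit or at every visit. A result significant at one or two visits would therefore have no pre-specified meaning for the primary hypothesis, and the reading could be chosen after the data are seen.

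**Working it through.** **1. What the formula sizes.** The Step 1 formula is N = 2(z₁₋α/₂ + z₁₋β)²[1+(T−1)ρ]/(d²T). The part [1+(T−1)ρ]/T is the variance of the mean of T equally correlated scores relative to one score. With T=3 and ρ=.7 it is (1 + 2×.7)/3 = 0.80. The formula therefore sizes one comparison of the follow-up average.

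**2. The plan's own figure.** With d=.38:
- Two-sided .05, as stated: 2(1.960+0.842)²×0.80/0.1444 = 86.97, so 87 per group.
- One-sided .05: 2(1.645+0.842)²×0.80/0.1444 = 68.5, so 69 per group.

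The printed 69 follows only from the one-sided critical value. That is a separate error. Results are shown below for both sizes, so that the present point does not depend on it.

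**3. Effective analysed sizes.** bCBT: 145×0.75/1.25 = 87. EUC: 80×0.75 = 60. These apply the full one-year attrition at every visit.

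**4. Power, unadjusted two-sided .05, d=.38 at each visit, ρ=.7.** Let v = 1/n₁ + 1/n₂ with SD 1. At 87 and 60, v = 0.02816.
- Average: Φ(.38/√(0.80v) − 1.960) = Φ(2.532 − 1.960) = 71.6%.
- One visit: Φ(.38/√v − 1.960) = Φ(2.264 − 1.960) = 62.0%.
- All three: the probability that three normal statistics with mean 2.264 and correlation .7 all exceed 1.960 = 43.3%.

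| Sizes | Average | One visit | All three |
|---|---|---|---|
| 69 / 69 (printed) | 70.4% | 60.7% | 42.0% |
| 87 / 60 (effective) | 71.6% | 62.0% | 43.3% |
| 87 / 87 (two-sided answer) | 80.0% | 70.8% | 53.7% |

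The gap from the average is 9–10 points for one visit and 26–28 for all three. For 80% power, the average needs 87 per group, one visit 109 and all three about 143.

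**5. Baseline adjustment at 87 / 60.** The plan gives no baseline-to-follow-up correlation, so a range of .3 to .7 is assumed. The upper end is the plan's repeated-measures figure; the entry cut-off of 10 on the GAD-7 may lower it. With correlation r, the residual variance is 1−r² and the covariance between visits is .7−r².

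| r | Average | One visit | All three |
|---|---|---|---|
| .3 | 77% | 66% | 47% |
| .5 | 86% | 74% | 55% |
| .7 | 98% | 89% | 75% |

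**6. Gradual dropout.** If the 25% loss accrues evenly over the year (an assumption), retention is 91.7% at month 4 and 83.3% at month 8. Effective sizes are then 106/73 and 97/67, and unadjusted single-visit power is 71% at month 4, about 67% at month 8 and 62% at month 12.

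**7. Match to the analysis text.** Neither the 12-month difference nor the time-by-treatment interaction is the average over months 4, 8 and 12. No contrast for that average is described in either document.

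**The case against.** A reader might infer that the hypothesis demands a significant result at all three visits, and so that the trial would more likely than not fail even if the planned effect is real. The documents do not support this. The phrase listing the three assessments can equally be read as the follow-up schedule, and no rule requires three significant results. The pessimistic conclusion also depends on unadjusted tests or a low baseline correlation: all-three power is 55% at a correlation of .5 and 75% at .7. The planned model does use baseline, as one of its four time points.

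Three further objections have force. First, separate tests by visit are no more part of the planned analysis than the average is; the model centres on the interaction. Second, at a baseline correlation of .7 a single visit reaches 89%, above the nominal 80%. Third, 62% understates months 4 and 8 unless all dropout comes before month 4.

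These points limit the size of the problem but do not remove it. Step 1 takes no credit for baseline, so adjustment cannot be what supports its 80%. The formula does not size the interaction either, and a significant interaction would not by itself establish superiority at each visit. If the average over follow-up was meant all along, the plan still has to say so and to test it.

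**Conclusion.** The concern holds as a mismatch between the quantity sized and the tests and hypothesis named. The 80% refers to the difference averaged over three visits, and the plan names no test of that average. For an unadjusted test at one visit the loss relative to the average is about 9–10 points, and it persists when the critical value is corrected. Measured from the stated 80% instead, single-visit power of 62% at the effective sizes is 18 points short, but about half of that comes from the separate critical-value error.

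The 26–28 point loss for significance at every visit is conditional on a rule that the documents do not contain, and should be quoted only with that condition. All the unadjusted figures assume an effect of .38 at each visit and a common correlation of .7, as the formula does. The adjusted range rests on an assumed baseline correlation. Across that range the average remains the best powered of the three options, and the all-visit claim stays below 80%.

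**What to change.** State in protocol 3.0 and 5.6 that the sized quantity is the bCBT–EUC difference in GAD-7 averaged over months 4, 8 and 12. In protocol 5.6 and the SAP, make the confirmatory GAD-7 test the baseline-adjusted version of that difference, taken as one contrast from a mixed model with visit as a category. Report the 4-, 8- and 12-month differences with confidence intervals as supporting results. Restate the power for this contrast with the two-sided critical value: at the planned numbers it is 72% unadjusted, and 77–98% with baseline adjustment under the assumed correlations.

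If superiority at a named visit or at every visit is kept as the claim, write down the success rule and restate its power instead.

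The change needs no added patients, visits or data, but it is more than one extra contrast. The primary model moves from a fitted line per participant to visit as a category, and the confirmatory claim becomes one about the year on average, with visit-specific claims secondary.

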Step 3: Provider Inflation Factor. The bCBT sample size was then inflated to account for the intraclass correlation due to clustering of patients within providers⁴³. We also will adjust the sample sizes for both the bCBT and EUC groups to account for attrition. Because only participants receiving bCBT are assigned to a provider, we first determined the average number of bCBT patients per provider (87 bCBT patients/25 providers = 3.5 patients per provider). To account for clustering in the bCBT group, the number of bCBT patients is inflated by the factor $[1 + (\bar{m} - 1) c]$, where \bar{m} is the average number of bCBT patients per provider and c is the correlation among patients seen by the same provider. Based on the sample size of 87 bCBT patients and an assumed correlation among patients of .10⁴³, our inflation factor is 1.25 ($87 \times 1.25 = 109$). Finally, to account for attrition, we assumed an attrition rate at 1 year of 25% ($109 \times (1/0.75) = 145$) gives 145 bCBT patients. A similar clustering inflation factor was not used for the EUC group, as no providers are assigned. Attrition rate of 25% was assigned to the EUC group ($58 \times (1/0.75) = 78$), rounded to 80 for randomization. The final number of randomized patients equates to 225 (145 bCBT and 80 EUC).

Secondary Aims:

Prediction of bCBT response and VVC-H use (bCBT group only). To assess predictors of bCBT response and VVC-H use, at least 10 events per variable in the logistic-regression models are needed to have unbiased estimates of the sample variance of the regression coefficients⁴⁴. No sample-size calculations were conducted for secondary aim, but SAS[®] proc power (version 9.4)⁴⁵ indicated a sample of 145 is adequate for 80% power to test odds ratio of 2.5, and conservative estimates for sample size and assumptions necessary to run the analyses suggest the project will be appropriately powered for 10 variables⁴⁶. Secondary analyses will include 8 variables for aim 2A (bCBT response; model #1) and 8 variables for aim 2B (VVC-H prediction; model #2).

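### Step 1 of the GAD-7 sample size does not follow from its own formula: the stated inputs give 87 per group (174), not 69 (138), so 225 patients give about 71–72% power at d = 0.38 for the comparison it describes

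*Protocol*

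**What the plan says.** The calculation is in Protocol 5.6, Sample Size and Power Calculations. Step 1 says: "A sample size of 138 anxiety patients is needed to detect an effect size = 0.38", and names the test as "using a two-sided t-test with 80% power at the .05 significance level, adjusted for repeated measures". It prints a formula for the number per group and says that its two Z terms "are the $(1-\alpha/2)$ and $(1-\beta)$ percentiles of the normal distribution", so the critical value is the two-sided one. The inputs are T = "three follow-up measurements after baseline", d = 0.38 and rho = .7. The result "yields a sample size per group of 69, and total sample" of 138.

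Step 2 takes N = 138 into a 1.5:1 allocation and reaches 145 (58 EUC, 87 bCBT). Step 3 multiplies the bCBT arm by 1.25 for clustering within providers and divides both arms by 0.75 for attrition: "The final number of randomized patients equates to 225 (145 bCBT and 80 EUC".

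The quality-of-life calculation needs only 80 patients, so the protocol lets the GAD-7 step set the total. The SAP's Data Analysis Plan, as available, refers to a sample-size section but contains no calculation that would replace this one. Neither document states a one-sided test.

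**The concern.** Everything needed to check Step 1 is printed beside it, and the result does not come out. The gap of 18 patients per group (87 − 69, or 21% of 87) is too large for rounding. It sits at the head of the chain. The later inflation factors are spent on unequal allocation, clustering and attrition, so none of them repairs it.

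The protocol presents 225 as the number needed to draw conclusions on the primary hypothesis. If that number has less than the stated 80% power at the planned effect, a null GAD-7 result would be read with more confidence than the design supports.

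**Working it through.** **Inputs (Protocol 5.6).** Two-sided alpha .05, so Z = 1.960; power 80%, so Z = 0.842; T = 3; rho = .7; d = 0.38; k = 1.5; provider correlation .10; 87/25 = 3.5 patients per provider; attrition 25%; final arms 145 bCBT and 80 EUC.

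**Step 1 as printed.** N = 2 × (Z(1−alpha/2) + Z(1−beta))² × [1 + (T−1)rho] / (d² × T)

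- With 1.960: 2 × (1.960 + 0.842)² × 2.4 / (0.1444 × 3) = 86.97, so 87 per group, 174 in total.
- With 1.645: 68.50, so 69 per group, 138 in total. This matches the protocol.

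**Other single changes that also return 69, keeping two-sided .05.**

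- Power 70% instead of 80%: 68.4.
- rho = .45 instead of .7: 68.8.
- d = 0.427 instead of 0.38: 68.9.

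**The quality-of-life step, for comparison.** If 7 is read as the mean difference and 11 as the SD, the normal approximation gives 39 per group two-sided and 31 one-sided. The protocol states 40, which fits a two-sided test. On that reading, the mismatch with a two-sided test is confined to the GAD-7 step.

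**The plan's chain from 138.** 138 × 2.5² / (4 × 1.5) = 143.75, stated as 145, split 58/87. Then 87 × 1.25 = 109 and 109/0.75 = 145; 58/0.75 = 77.3, taken as 78 and rounded to 80. The total is 225. Steps 2 and 3 therefore follow from 138 apart from small rounding.

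**What 225 delivers for the Step 1 comparison.** The averaged follow-up mean has variance factor (1 + 2 × 0.7)/3 = 0.80.

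- After 25% attrition: 145 × 0.75 = 108.75 bCBT, and 80 × 0.75 = 60 EUC.
- Effective bCBT after clustering: 108.75/1.25 = 87.
- SE = sqrt(0.80 × (1/87 + 1/60)) = 0.150.
- Power = Phi(0.38/0.150 − 1.96) = 71.6% (71.1% with the t distribution).
- Effect detectable with 80% power: 2.802 × 0.150 = 0.42.

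**Sensitivity of the power figure (two-sided, d = 0.38).**

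| Case | Power |
|---|---|
| 69 per group, as in Step 1 | 70.4% |
| 58/87, as in Step 2 | 70.8% |
| Final 225, attrition and factor 1.25 | 71.6% |
| Same, factor 1.336 (109/25 = 4.36 per provider) | 70.4% |
| Same, 32 providers (108.75/32 = 3.4 per provider, factor 1.24) | 71.8% |
| Final 225 with attrition, clustering ignored | 75.2% |
| Final 225, no attrition, factor 1.25 | 83.2% |

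**The plan's chain from 174.** 174 × 6.25/6 = 181.25, so 73 EUC and 109 bCBT. With the 1.25 factor: 109 × 1.25/0.75 = 181.7, so 182, and 73/0.75 = 97.3, so 98; about 280 in total. With factor 1.336 the bCBT arm is 195 and the total about 293.

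**The case against.** **The cause is not established.** A reader might infer that the trial was sized for a one-sided test. The documents do not support stating that as fact: both the text and the formula say two-sided, and a power of 70%, rho of .45 or d of 0.427 also gives 69. If rho or d is what was misprinted, 69 per group does have 80% power under the intended input. This stands. What is shown is that the inputs and the result disagree, with 1.645 as the most plausible explanation.

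**71–72% is not the power of the planned analysis.** A reader might infer that the trial has nearly a 3-in-10 chance of missing the planned effect. That holds for the comparison that Step 1 describes, which ignores baseline. The primary analysis in both documents is a mixed model on four time points, baseline included, with the time-by-treatment interaction as the term of most interest. If rho = .7 also held between baseline and follow-up (an assumption), the mean change from baseline would have variance factor 0.80 + 1 − 2 × 0.7 = 0.4, and power would be about 95% at 87/60. A linear-slope interaction could differ in either direction. This stands as a limit on the claim. It does not rescue the stated 80%, because the protocol justifies 225 by the Step 1 formula alone.

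**Attrition is counted as total loss.** The 25% is a one-year rate, and the model keeps patients with partial follow-up, so 71–72% is the cautious end and 83% the other. The 25% convention is nevertheless the plan's own.

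**Cluster size is uncertain.** Section 5.1 and Step 3 use 25 providers, while section 5.2 gives a recruitment target of 32. Neither can be called the size the trial will have. It matters little: power is 70.4% with the 1.336 factor based on 25 providers and 71.8% with 32.

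**Conclusion.** The point holds. With the stated inputs, Step 1 gives 87 per group (174), not 69 (138), and the shortfall runs through to 225. On the plan's 25% attrition and 1.25 clustering factor, the comparison of averaged follow-up means has about 71–72% two-sided power at d = 0.38, or 80% at about 0.42. Without attrition, power would be about 83%.

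These power figures assume that the printed d and rho are the intended ones. Two further inferences go beyond the documents: that a one-sided test was planned, and that 71–72% is the power of the mixed-model interaction. Nor does it follow that about 280 patients must be randomised. That is what the plan's chain would require to keep 80% at 0.38, and stating the true power of 225 is enough.

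**What to change.** In Protocol 5.6, correct Step 1 to 87 per group (174 in total). If another input was intended, correct that input and give its source. Then restate what 225 delivers under the plan's attrition and clustering: about 71–72% power at d = 0.38, or 80% at about 0.42, two-sided .05. Say that this refers to the averaged follow-up difference and that no power has been calculated for the time-by-treatment interaction. Carry the same statement into the SAP where it refers to sample size.

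The cost is wording and a less favourable stated power. No extra patients are needed.

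Optionally, a baseline-adjusted comparison may recover some power. The variance factor becomes 0.80 − r², where r is the baseline/follow-up correlation. At 87/60 effective, power is about 77%, 81% and 86% for r = .3, .4 and .5. The documents give no value for r, so these are assumptions. Replacing the interaction with this comparison would also change the primary analysis, in which baseline already enters as a time point. It would have to be specified before outcomes are seen by arm, and it is not part of the required correction.
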